All subjects will undergo at minimum a 10-week OTTP even if the optimized dose and regimen is achieved earlier. Every effort should be made to titrate to an optimally effective and tolerable dose and regimen within the first 8 weeks, and maintain an unchanged dose of JZP-258 for at least 2 weeks prior to entering the SDP. Any subject for whom an efficacious and tolerable dose and regimen is not established within the first 10 weeks may undergo up to an additional 4-weeks of titration/adjustment with approval from the Medical Monitor. Subjects who are unable to attain an efficacious and tolerable dose and regimen after 14 weeks will be withdrawn from the study.

Subjects who have reached an optimized dose and regimen, and who have completed the OTTP, will then enter the 2-week SDP.

Stable Dose Period (2 weeks)

Subjects will remain on the stable JZP-258 dose, unchanged, during this 2-week period. Upon completion of the SDP, subjects will be assessed for randomization eligibility.

Double-blind Randomized Withdrawal Period (2 weeks)

Subjects who meet the randomization eligibility criteria at the end of the SDP will be randomized if the following conditions are met at the End of Stable Dose Visit:

- The dose and regimen of JZP-258 remains unchanged during the SDP, and subjects demonstrate adequate compliance with dosing.
- No ongoing adverse events (AEs) occur due to JZP-258 treatment that would require dose adjustment or treatment discontinuation during the DBRW.
- Subjects who are on Xyrem at study entry must have PGIc scale ratings at the end of the SDP of no change, minimal, much, or very much improved compared with the Baseline Visit.
- Subjects who are not on Xyrem at study entry must have PGIc scale ratings of minimal, much, or very much improved compared with the Baseline Visit and a lower ESS score at the end of the SDP compared with the Baseline Visit.

Eligible subjects are randomized 1:1 to receive 1 of the following 2 treatments during the 2-week DBRW.

- JZP-258: Active JZP-258 will be continued as a double-blind (DB) treatment at the stable dose and regimen for 2 weeks.
- Placebo: Placebo will be initiated as a DB treatment at a volume and regimen equivalent to the JZP-258 dose and regimen for 2 weeks.

Open-label Safety Extension Period (24 weeks)

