5.3. Study Treatment

During the OTTP, all subjects will receive open-label JZP-258 and are titrated to a tolerable and efficacious dose based on the recommendations summarized in Table 1.

Table 1: JZP-258 Dosing Recommendations

Dosing Regimen	Starting Nightly Dose	Titration Increments	Maximum Nightly Dose ^b
Once Nightly	≤3 g	≤1.5 g/night per week	6g
Twice Nightly	≤4.5 g (divided)	≤1.5 g/night per week	9g
Thrice Nightly (titration only, not a starting dose)	Not applicable	≤1.5 g/night per week	9g

Note: the aim of JZP-258 dose titration and optimization is to maximize efficacy (reduced IH symptoms, e.g. EDS, sleep inertia, and sleep duration) while ensuring adequate nocturnal sleep and minimizing risks associated with safety and tolerability

^aThe weekly increase in dose of ≤1.5 g/night may be made incrementally every few days as tolerated

^bThe maximum single dose should not exceed 6 g and the maximum nightly dose should not exceed 9 g at twice or thrice nightly dosing

EDS=excessive daytime sleepiness; IH=idiopathic hypersomnia

During the SDP, all subjects will receive open-label JZP-258 at the same unchanged dose that they received at the end of the OTTP.

During the DBRW, all subjects will receive blinded study drug. At the end of the SDP, subjects will enter the DBRW and will be randomized 1:1 to receive either JZP-258 (at the dose taken at the end of the SDP) or Placebo (at a volume and regimen equivalent to the JZP-258 dose taken at the end of the SDP).

During the OLE all subjects will receive open-label JZP-258. During the PK study, all enrolled subjects will receive open-label JZP-258 with no change in dose required.

Study drug will be dispensed at clinic visits and, if applicable, at intervals specified by state or local regulations or to resolve logistical issues.

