10.1. Exposure

10.1.1. Extent of Exposure

The below exposure information will be summarized based on the SAF using descriptive statistics as well as counts and percentages, as appropriate, depending on the study period. Exposure summaries are based on data collected by the study drug administration eCRF.

- **Across all periods overall and by Baseline Medication Group:** average of total nightly dose of JZP-258 (in g/night), duration of exposure to single doses of JZP-258 > 4.5g, duration of study drug exposure in days, and duration of exposure to JZP-258 in days (excludes time subjects received Placebo in DBRW);
- **Across all periods by Stable Dose Regimen (once nightly vs twice nightly):** starting dose regimen of JZP-258 in OTTP (once, twice, or thrice nightly), time to get to total nightly stable dose (in days), average of total nightly dose of JZP-258 (in g/night), and duration of exposure to JZP-258 (in days);
- **OTTP overall and by Baseline Medication Group:** total nightly starting dose of JZP-258 (in g/night), average of total nightly dose of JZP-258 (in g/night), starting dose regimen of JZP-258 (once, twice, or thrice nightly), number of dose adjustments, time to get to total nightly stable dose (in days), and duration of exposure (in days) regardless of the JZP-258 total nightly received dose;
- **SDP overall and by Baseline Medication Group:** average of total nightly dose of JZP-258 (in g/night) and duration of exposure (in days) regardless of the JZP-258 total nightly received dose;
- **DBRW overall and by Baseline Medication Group:** JZP-258 total nightly received dose (in g/night), and duration of study drug exposure (in days) regardless of the study drug total nightly received dose;
- **SDP and DBRW by Randomized Treatment group:** JZP-258 total nightly received dose (in g/night), duration of exposure (in days) regardless of the JZP-258 total nightly received dose in SDP, and duration of study drug exposure (in days) regardless of the study drug total nightly received dose in DBRW;
- **OLE overall and by Baseline Medication Group:** average of total nightly dose of JZP-258 (in g/night) and duration of exposure (in days) regardless of the JZP-258 total nightly received dose

Exposure summaries reflect all dose changes entered on the study drug administration eCRF. Data from the dosing diary and compliance are not considered for duration of exposure.

Listings of study drug exposure and of the dosing diary will be presented.

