10.2.2. Additional Adverse Event Analyses

The subject incidence of TEAEs up to 30 days after last dose (excluding AEs during the DBRW for those randomized to Placebo as well as AEs up to 30 days after last dose of Placebo for those not entering OLE) by 4 week intervals across the study will be summarized by Baseline Medication Group and overall using the SAF. Additionally, results will be presented for week 1, week 2, week 3, and week 4 during the OTTP. These analyses will be summarized by SOC and PT. A subject will be counted in each interval (once per onset) that a TEAE occurred within the interval and the denominator for the interval is based on the number of subjects who were exposed to study drug at the start of the interval. Ongoing TEAEs will only be counted once in the interval of onset.

The subject incidence of TEAEs by SOC and PT during the 30 day period after the last dose of JZP-258 will be summarized by Baseline Medication Group and overall using the SAF. This summary will exclude adverse events during the 30 day period after the last dose of Placebo for those randomized to Placebo who did not receive study drug during the OLE.

Additional adverse event summaries for those subjects exposed to a single dose of JZP-258 of > 4.5g at any time during the study will be provided and compared against the full SAF analysis set. The group of subjects' exposure to a single dose of JZP258 of > 4.5g can include receiving any dose regimen, as long as one of the doses was > 4.5g.

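### SAP 10.2.2: the 4-week-interval TEAE table drops placebo-period events but keeps the placebo subjects in its denominator, understating JZP-258 incidence by up to about a quarter around the randomized withdrawal period

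*SAP*

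**What the plan says.** SAP 10.2.2 (Additional Adverse Event Analyses) presents TEAE incidence "by 4 week intervals across the study will be summarized by Baseline Medication Group and overall using the SAF".

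- **Numerator.** It is restricted by "excluding AEs during the DBRW for those randomized to Placebo as well as AEs up to 30 days after last dose of Placebo" for placebo subjects who do not go on to the open-label extension (OLE).
- **Denominator.** The same paragraph says "the denominator for the interval is based on the number of subjects who were exposed to study drug at the start of the interval". No matching exclusion of placebo subjects or placebo days is stated there or elsewhere in SAP 10.2.
- **Meaning of study drug.** SAP 5.3 says "During the DBRW, all subjects will receive blinded study drug". SAP 10.1.1 lists two separate exposure measures: "duration of study drug exposure in days, and duration of exposure to JZP-258 in days (excludes time subjects received Placebo in DBRW"). Only the second removes placebo time. Protocol 5.1 points the other way: it labels JZP-258 as the study drug and lists placebo as a separate item.
- **Design.** "Eligible subjects are randomized 1:1 to receive 1 of the following 2 treatments during the 2-week DBRW" (SAP 5.1). Titration lasts 10 to 14 weeks and the stable dose period (SDP) 2 weeks. All subjects receive open-label JZP-258 in the OLE. Protocol 7.2 expects titration to end at week 10 for most subjects.

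**The concern.** Removing placebo-period events shows that the table is meant to describe adverse events on JZP-258 over time. For that, the numerator and denominator must cover the same subject-time. As written they do not. A placebo subject on the usual schedule is counted as a full member of the interval holding the DBRW, although for about half of that interval nothing that happens to the subject can enter the numerator.

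At stake is the reading of one safety time-course table. The interval percentages around the DBRW would not be comparable with those before and after it. The affected interval is also the one in which most placebo subjects restart JZP-258 after two weeks off it.

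**Working it through.** The plan gives no figure for this table, so there is none to reproduce. The size follows from the calendar.

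**Inputs from the documents.** Randomized subjects: 112, 56 per arm (SAP 5.4). Allocation 1:1. Interval 28 days. SDP and DBRW 14 days each. Titration 70, 84 or 98 days.

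**Assumptions.** Intervals run from Study Day 1. Everyone in the interval is randomized and completes it. The hazard on JZP-258 is constant where subject incidence is computed. The share extending titration is not given in the documents, so a range is shown.

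**Calendar.** The DBRW occupies study days T+15 to T+28, where T is titration length in days.

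| Titration | DBRW days | Interval containing it |
|---|---|---|
| 10 weeks | 85-98 | 85-112 (weeks 13-16) |
| 12 weeks | 99-112 | 85-112 (weeks 13-16) |
| 14 weeks | 113-126 | 113-140 (weeks 17-20) |

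**Subject-time, all at 10 weeks.** Denominator: 112 × 4 = 448 subject-weeks. Time that can contribute events: 56 × 4 + 56 × 2 = 336. Barred: 112/448 = 25.0%.

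**Subject incidence, all at 10 weeks.** With true 4-week incidence p, a continuing subject has probability p. A placebo subject with 14 countable days has 1 − (1 − p)^(14/28). The table shows the mean of the two.

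| True | Shown | Shortfall |
|---|---|---|
| 5% | 3.8% | 24.7% |
| 10% | 7.6% | 24.3% |
| 30% | 23.2% | 22.8% |
| 50% | 39.6% | 20.7% |

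**Day-1 attribution.** SAP 10.2 assigns an event on the day the DBRW starts to the preceding period, so such an event is still counted. Strictly, 13 days are barred (86-98). At p = 10% the placebo term is 1 − 0.9^(15/28) = 0.0549, and the table shows (0.1000 + 0.0549)/2 = 7.7%, about 23% low.

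**Extended titration.** On nominal days only the share q going to week 14 matters. The shortfall in subject-time is 25% × (1 − q) in weeks 13-16 and 25% × q in weeks 17-20.

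| Share to week 14 (assumed) | Weeks 13-16 | Weeks 17-20 |
|---|---|---|
| 0% | 25% | 0% |
| 20% | 20% | 5% |
| 30% | 17.5% | 7.5% |
| 50% | 12.5% | 12.5% |

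**Visit windows.** With SDP and DBRW visits spread evenly over 14-17 days (an assumed spread within the Protocol Appendix 1.1 windows) and no extension, simulation gives about 26-28% in weeks 13-16.

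**Study drug read as JZP-258 only.** If every placebo subject is already on placebo when the interval opens, the denominator falls to 56. Their open-label events on days 99-112 remain in the numerator. At p = 10% the ratio to truth is (56 × 0.1000 + 56 × 0.0513)/(56 × 0.1000) = 1.51. This is an extreme case. SAP Table 3 puts randomization on day 85, the first day of the interval, so an SDP one day longer leaves the subject on JZP-258 at interval start and in the denominator under either reading.

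**The case against.** **The size is not fixed.** This stands. A quarter is the nominal 10-week case; extension of titration lowers it in weeks 13-16 and moves part of it to weeks 17-20, and for common events it is nearer a fifth.

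**A reader might infer a dip at weeks 13-16 and a rebound at weeks 17-20 that would be mistaken for tolerance, hiding risk at restart.** The documents do not support going that far. For 14-week titrators the deficit lies in weeks 17-20, and if half the subjects were such, both intervals would be equally low. Restart events on open-label JZP-258 are counted. If the hazard on restart were double that of continuing subjects, 14 days at twice the rate would equal 28 days at the usual rate and no dip would appear. What remains is narrower: the percentage is diluted by time that cannot contribute.

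**The table is supplementary.** True: SAP 10 plans no safety inference, SAP 10.2 reports DBRW events by arm, and all adverse events are listed. A start-of-interval denominator is also a common convention. But that convention does not normally accompany a numerator from which part of the denominator's time has been deliberately removed, and the by-arm table stops at the first OLE dose, so it does not repair this one.

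**Study drug may mean JZP-258 only.** Protocol 5.1 gives some support, but SAP 5.3 and 10.1.1 use the term to include placebo, and the narrower meaning does not align numerator and denominator either.

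**Conclusion.** The rule in SAP 10.2.2 is mismatched as written and understates JZP-258 incidence in the interval or intervals holding the DBRW. The shortfall in weeks 13-16 is up to about a quarter if all subjects end titration at week 10 (10% shows as about 7.6-7.7%). It is roughly 12-20% if 20-50% extend to week 14, with about 5-12.5% then falling in weeks 17-20. These sizes rest on 1:1 allocation, nominal visit days, full retention and, for subject incidence, a constant hazard. On the narrower meaning of study drug the error can run upward, by an amount that depends on exact visit days.

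A lesser, unquantified mismatch lies in the same paragraph: events count up to 30 days after the last dose, which is longer than a 28-day interval. A subject who stopped in one interval can therefore appear in the next numerator without being in its denominator.

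The point is confined to this descriptive table.

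**What to change.** In SAP 10.2.2, choose one of two forms:

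- keep calendar intervals and report subjects with events per JZP-258 person-time at risk in each interval, excluding placebo days; or
- define the 4-week intervals on cumulative days of JZP-258 exposure, so that placebo days do not advance the clock.

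On calendar intervals it is not enough to redefine the denominator as subjects with any JZP-258 exposure in the interval. A 10-week titrator on placebo is back on JZP-258 for days 99-112 and would still count in full, leaving the bias in place.

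Report events after the last JZP-258 dose only in the separate 30-day post-dose table that the same section already plans.

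The cost is SAP wording and a changed denominator in one table. No new data are needed, since SAP 10.1.1 already derives JZP-258 exposure without placebo time. The small downside is that exposure-based intervals no longer match calendar study weeks for placebo subjects.

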2. MODIFICATION HISTORY

Version History for SAP:

Version	Date	Description & Rationale for Change
Version 1.0	06-Dec-2019	Original SAP
Version 2.0	31-Aug-2020	
The purpose of this amendment is the following:
 
 - Summarize changes in study conduct due to COVID-19 restrictions as well as the additional analyses for efficacy, safety and protocol deviations - This study was originally designed to include an optional interim analysis for efficacy. The SAP has been updated to confirm that the interim analysis was not performed - Additional analyses have been added to further understand the demographic, baseline and disease characteristics, exposure, and adverse events of subjects receiving JZP-258 once nightly and single doses of JZP-258 >4.5g. - The list of adverse events of special interest have been updated to include the category Accidents and Injuries because this known oxybate effect has not been fully evaluated in a patient population without cataplexy as a confounder. - Additional minor clarifications were made to align with the specifications for analysis.

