6. ANALYSIS SETS

For the purpose of analysis, the following populations are defined:

Table 2: Analysis Sets

Analysis Set	Description
All Screened	
The all screened analysis set (SCR) will contain all subjects who provided a signed informed consent for this study.
 
This analysis set will be used to summarize the number of screened, screen failure and enrolled subjects.

Analysis Set	Description
Enrolled	
The Enrolled Analysis Set (ENR) will contain all subjects who provided a signed informed consent form (ICF) for this study and were deemed as meeting the inclusion/exclusion criteria of this study by the Investigator and were dispensed study drug.
 
This analysis set will be used to summarize subject disposition, major protocol deviations as classified in the Clinical Trial Management System (CTMS) [the study CRO, IQVIA, manages the CTMS], and inclusion/exclusion from each analysis set.

Safety	
The overall Safety Analysis Set (SAF) will include all subjects who took at least one dose of study medication. The SAF will also be defined for each study period:
 
 • The OTTP SAF will contain all subjects in the ENR who took at least one dose of open label (OL) study drug during the OTTP. Hence, the OTTP SAF will be the same as the overall SAF. • The SDP SAF will contain all subjects in the ENR who took at least one dose of OL study drug during the SDP. • The DBRW SAF will contain all subjects in the ENR who took at least one DB study drug. • The OLE SAF will contain all subjects in the ENR who took at least one dose of OL study drug during the OLE. 
The overall SAF will be used to summarize subjects' demographic and other baseline characteristics data, past medical conditions/diseases, surgical history, medications, IH diagnosis history data as well as exposure to study drug and all safety data; select outputs will also be provided for the DBRW SAF.

Randomized	
The Randomized Analysis set (RND) includes all randomized subjects. Subject disposition for the DBRW will be summarized using this analysis set.

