10. SAFETY

Safety analyses will be based on the SAF and summarized across all study periods by Baseline Medication Group. In addition, data from the DBRW will be summarized by treatment group using the DBRW SAF. No inferential statistical analysis will be performed; only descriptive summaries will be provided.

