10.2. Adverse Events

Adverse events (AEs) occurring from the initial subject ICF signature date until the final study visit will be reported. If the Investigator becomes aware of a serious adverse event (SAE) within 30 days after the last dose of study drug, the event must also be reported. In addition, any SAE assessed as related to study drug or procedure by the Investigator must be reported regardless of time after study termination.

AEs will be coded to system organ class (SOC) and preferred term using the Medical Dictionary for Regulatory Activities (MedDRA), Version 19.1. The investigator will assess the relationship of each AE to study drug. AE with a missing relationship to study drug will be reported as related in the summaries. Severity, as determined by the Investigator, will be classed as mild, moderate, severe, life-threatening or fatal. AE with missing severity will be reported as missing in the summaries.

Note that subjects who acquire COVID-19 or report AEs due to the COVID-19 public health emergency (e.g. anxiety) while on study will be coded accordingly and included in the adverse event summaries.

All AEs will be classified according to the period onset as defined by the following:

- Screening AEs are defined as AEs that started on or after the signature of the initial subject ICF but prior to or on the first dose of OTTP study drug
- Treatment period AEs will be defined as occurring in treatment periods (OTTP, SDP, DBRW, and OLE) based on the onset date and the date of first dosing in each of the treatment periods. AEs that occur on the start of the SDP and DBRW are attributed to the previous period.
- Safety follow-up AEs are defined as occurring after the last dose date until 30 days after the last dose date

A treatment-emergent adverse event (TEAE) is defined as any event with onset date on or after the first dose of study drug, including adverse events that occur until 30 days after the last dose date. For the purpose of calculating treatment emergence, incomplete onset dates will be imputed as detailed in Appendix 2.

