Only TEAEs are included in summary tables unless otherwise specified. If a subject has multiple episodes of events coded to the same SOC or PT, then the subject will be counted just once in the summaries for that term. Subject incidence of TEAEs by SOC and PT tables are sorted by SOCs (alphabetical order) and then by PTs (descending order) within each SOC for the overall frequency. For summaries by PT only, PTs will be sorted in descending order of overall frequency.

Each TEAE summary will have two sets of outputs:

- TEAEs by baseline medication group across the entire study (excluding adverse events during the DBRW for those randomized to Placebo) up to 30 days after last dose using the SAF

- TEAEs during the DBRW by randomized treatment group using the DBRW SAF. Adverse events are included as TEAEs up to 30 days after the last dose date or the first dose date in the OLE period, whichever is earlier.

A general overall summary of TEAEs with the number and percent of subjects who experienced the following types of events will be provided:

- Subjects with any TEAE
 - Subjects with any related TEAE
- Subjects with any serious TEAE
- Subjects with TEAE by severity
- Subjects with an AE outcome as death
- Subjects with any TEAE leading to study drug discontinuation
- Any TEAE leading to study drug dose reduction
- Any TEAE leading to study drug dose increase
- Any TEAE leading to study drug dose interruption
- Any TEAE not recovered

Subject incidence of TEAEs tables will be summarized by the following:

- SOC and PT
 - TEAE reported $\geq 2\%$ of by SOC and PT
- PT only
- Maximum severity by SOC and PT
- Treatment-related by SOC and PT
- TEAEs of special interest by category (defined in section 10.2.1) and PT
- TEAEs leading to permanent withdrawal of study drug by SOC and PT

Separate adverse event listings will be provided including the following:

- All adverse events
- Adverse events with an outcome of death
- Adverse events leading to permanent withdrawal of study drug
- Serious adverse events
- Adverse events of special interest, defined in section 10.2.1

Non-TEAEs will be flagged in the listings.

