All data collected on the electronic case report form will be presented in the data listings. The listings will be ordered by the following (unless otherwise indicated in the shells): randomized treatment group, Baseline Medication Group, subject number, date (where applicable), and time (where applicable).

For listings where non-randomized subjects are included, these will appear in a category after the randomized treatment groups labeled 'Not Randomized'.

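### The adverse-event summary for single doses above 4.5 g uses a comparator that contains the exposed subjects and, by default, counts events from before the first such dose; a minor point, cheap to improve

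*SAP*

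**What the plan says.** SAP 10.2.2 plans additional adverse-event summaries for subjects exposed to a single JZP-258 dose above 4.5 g "at any time during the study will be provided and compared against the full SAF analysis set". Any dosing regimen qualifies, provided one of the doses was above 4.5 g. The comparator, the overall Safety Analysis Set (SAP 6), "will include all subjects who took at least one dose of study medication".

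The paragraph gives no onset rule of its own. SAP 10.2 defines a treatment-emergent event as "any event with onset date on or after the first dose of study drug", up to 30 days after the last dose, and restricts summary tables to such events unless something else is specified. It describes the main output set as "TEAEs by baseline medication group across the entire study", leaving out events in the double-blind period for subjects randomised to placebo.

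The Modification History (SAP 2) gives the purpose. Version 2.0 added analyses to further understand, among other things, "adverse events of subjects receiving JZP-258 once nightly and single doses of JZP-258 >4.5g". For safety as a whole, SAP 10 states: "No inferential statistical analysis will be performed; only descriptive summaries will be provided".

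**The concern.** There are two separate features of the layout.

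- **Overlap.** Every subject in the above-4.5 g column is also in the comparator column. The two percentages are pulled together by construction, and more strongly the larger the exposed share. No column of never-exposed subjects is planned.
- **Onset.** Membership depends on ever having had a single dose above 4.5 g, but events count from the first dose of any study drug. An event during early titration, before any dose above 4.5 g, then appears in the above-4.5 g column. The table does not separate it from events that follow such a dose.

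This is the only adverse-event summary by single-dose size in the SAP. A reader will use it to judge whether larger single doses come with more events. The two columns answer that less directly than the collected data would allow.

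**Working it through.** The documents give no figure for this summary, so there is nothing of the plan's to reproduce.

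**Step 1: overlap.** Let p_e be the subject incidence of a term among exposed subjects, p_n the incidence among never-exposed subjects, and f the exposed share of the SAF.

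- SAF incidence: p_SAF = f·p_e + (1 − f)·p_n
- Displayed difference: p_e − p_SAF = (1 − f)·(p_e − p_n)

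This is an identity and does not depend on event rates. Since f is not given, a range is shown:

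| Assumed f | Share of the exposed-minus-never difference that is displayed |
|---|---|
| 10% | 90% |
| 20% | 80% |
| 50% | 50% |
| 70% | 30% |

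Example with assumed incidences p_e = 30% and p_n = 15%, a true gap of 15 points:
- f = 20%: p_SAF = 0.2·30 + 0.8·15 = 18%, displayed gap 12 points.
- f = 50%: p_SAF = 22.5%, displayed gap 7.5 points.

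The missing column can be recovered: p_n = (p_SAF − f·p_e)/(1 − f). Equivalently, subtract exposed counts and Ns from the SAF counts and Ns. This is exact because SAP 10.2 counts each subject once per term, provided both columns use the same event rule.

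**Step 2: treatment time before the first dose above 4.5 g.** Inputs:
- New once-nightly starters begin at no more than 3 g and rise by at most 1.5 g/night per week (Protocol 5.3.1).
- Maximum treatment duration is about 38 to 42 weeks (Protocol 3.4).

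From 3 g, the dose can be at most 3 + 1.5 = 4.5 g after one week, which is not above 4.5 g. The first dose above it therefore falls in week 2 at the earliest, or after week 2 if increases are made in full weekly steps. The minimum share of treatment time is 1/42 = 2.4% to 2/38 = 5.3%, and more if the threshold is reached later.

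Subjects switching from Xyrem keep their existing regimen (Protocol 5.3) and may have no such period.

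**Step 3: illustration in the table's own unit, subject incidence.** Assumptions:
- Onset pattern over 38 weeks, t in weeks: (i) constant at 0.58/38 per week; (ii) 0.06 per week for 4 weeks, then 0.01; (iii) 0.01 + 0.08·exp(−t/2).
- Onsets are independent Poisson, and the rate doubles after a first dose above 4.5 g at the end of week 2.

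Let A be expected onsets in weeks 0 to 2 and B in weeks 2 to 38 without doubling. Then p_e = 1 − exp(−(A + 2B)) and p_n = 1 − exp(−(A + B)).

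| Pattern | A | B | p_e | p_n | p_e/p_n | p_e/p_SAF, f = 20% | p_e/p_SAF, f = 50% |
|---|---|---|---|---|---|---|---|
| (i) | 0.031 | 0.549 | 67.7% | 44.0% | 1.54 | 1.39 | 1.21 |
| (ii) | 0.120 | 0.460 | 64.7% | 44.0% | 1.47 | 1.34 | 1.19 |
| (iii) | 0.121 | 0.419 | 61.7% | 41.7% | 1.48 | 1.35 | 1.19 |

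So 1.47 to 1.54 against never-exposed subjects becomes 1.34 to 1.39 (f = 20%) or 1.19 to 1.21 (f = 50%) against the SAF. Within the exposed group, the share counted solely because of an event before the first dose above 4.5 g is (1 − exp(−A))·exp(−2B)/p_e, which is 1.5% to 8%. With no dose effect it is (1 − exp(−A))·exp(−B)/p_n, which is 4% to 18%. These figures illustrate direction and order of size. They do not predict this trial's results.

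**The case against.** **The SAP sets no exposed-versus-never contrast.** The stated aim is to understand events in subjects receiving these doses. Describing a subgroup beside the whole safety population is a legitimate way to do that. This stands: the layout is not an error against a stated estimand. It is a less informative choice for the question a reader will bring to it.

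**Nothing is lost.** Subtraction recovers the never-exposed column, and subject-level checks are possible. Adverse events are listed (SAP 10.2), "Listings of study drug exposure and of the dosing diary will be presented" (SAP 10.1.1), and "All data collected on the electronic case report form will be presented in the data listings" (SAP Appendix 1). This stands for the overlap. Subtraction cannot separate events before from events after the first dose above 4.5 g, although the listings can.

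**The onset point rests on silence.** Output shells are mentioned in SAP Appendix 1 but are not available here and might specify the layout. This stands as a limit: the conclusion is what happens by default.

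**f may be small.** An equal twice-nightly split of the 9 g maximum gives 4.5 g per dose, which is not above the threshold. At f = 10% the displayed difference keeps 90% of its size.

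**Never-exposed subjects are a selected group.** This also stands. The same selection is already inside the planned comparison, where it is less visible.

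A reader might infer that the table hides a dose-related safety signal, or that much of the above-4.5 g column is early-titration events. The documents support neither. They give no f and no event rates, and the only pre-exposure share that follows from them is the 2.4% to 5.3% minimum. First reaching a dose above 4.5 g in the extension is possible, since titration may continue there. It is an edge case, because subjects need an optimised regimen before the Stable Dose Period (SAP 5.1).

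**Conclusion.** Both features are present in the plan as written, and both are minor. The overlap reduces the displayed difference to (1 − f) of the exposed-minus-never-exposed difference. That factor is exact; only f is assumed. The onset feature follows from the general event rule in the absence of a specific one. For new once-nightly starters it covers at least 1 to 2 of 38 to 42 treatment weeks, and for some Xyrem switchers none. The incidence ratios rest on assumed onset patterns, an assumed doubling and independent Poisson onsets.

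The summary is descriptive. No test, error rate or trial decision depends on it, and the efficacy conclusions are untouched. The limitation lies in one supplementary table and is worth correcting because the correction is cheap.

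**What to change.** In SAP 10.2.2 and the corresponding shell:

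1. Add a column for SAF subjects never given a single dose above 4.5 g. Keep the full SAF column as context.
2. Within the above-4.5 g column, keep the whole-study total and add rows for TEAEs with onset before, and on or after, the first dose above 4.5 g. Footnote that the second row must not be compared with whole-study never-exposed incidence, because follow-up time differs.
3. Footnote that the groups are not randomised. Never-exposed subjects include early discontinuers, subjects kept at lower doses for tolerability, and subjects on equal twice-nightly splits, which cannot exceed 4.5 g per dose at the 9 g maximum.

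Do not add an exposed-versus-never comparison within the 4-week intervals of 10.2.2. It would classify subjects in early intervals by dosing that comes later. With about 140 enrolled subjects, it would also leave very small cells.

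The cost is a wording change and some programming from adverse-event onset dates and the dose changes already recorded on the study drug administration eCRF. No new data are needed. The remaining drawback is a non-randomised comparator, which is why the footnote in item 3 is required.
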